2.3.1.2 Other Echocardiographic Analyses

Other, secondary endpoints include:

- Number of subjects within each tricuspid or pulmonic regurgitation score by visit
- Number of subjects with normal ortrace tricuspid or pulmonic regurgitation at baseline and ≥ mild tricuspid or pulmonic regurgitation at end of study
- Pulmonary Artery Systolic Pressure (PASP)
 - o Mean change from baseline at end of study
 - Mean maximum change from baseline at anytime during therapy
 - Number of subjects with change from baseline at anytime during therapy shows:
 - > 10 mmHg
 - >15 mmHg
 - >20 mmHg

Number of subjects at anytime during therapy shows

- PASP>35 mmHg
- Right ventricular outflow tract(RVOT) (will be used only as confirmatory variables for pulmonary hypertension)

- o Mean Change from Baseline in RVOT (mmHg) by visit
- Number of patients with Baseline ≥100 msec and at EOS/ET RVOT
 <100 msec
- Number of patients with any RVOT measurement < 100 msec postbaseline

Summary of the number of ECHOs per subject will also be presented.

2.3.1.3 Heat Maps

Heat maps will be constructed for all valve scores to visualize longitudinal changes, if any, in regurgitation measures in individual subjects over time. An example of a heat map is shown below.

	Visit	Visit	Visit 12	Visit 14
Subject ID	1	8	EOS/ET	Follow-up
1001-001				A) 9
1001-002				
1001-003			R F	
1001-004				
1001-005			01, 14	

Note: different colors represent the valve scores such as No ECHO, Absent, Absent, Mild, Moderate, and Severe.

Heat maps will be constructed for all valve scores by age groups (\leq 18, >18 years).

2.3.2 ECG

2.3.2.1 Main Focus of ECG Analysis

The primary endpoint will be the mean change between measurements of QT interval corrected using Fridericia's formula (QTcF) for ZX008 (0.2 mg/kg and 0.8 mg/kg) and placebo after baseline adjustment, ($\Delta\Delta$ QTcF)

2.3.2.2 Other ECG Analyses

The secondary endpoints:

- Mean QTcF duration including changesfrom baseline (ΔQTcF)
- Mean QRS duration (including changes from baseline (Δ QRS) and from placebo and baseline (Δ QRS))
- Mean PR interval measurements (including changes from baseline (Δ PR) and from placebo and baseline (Δ DPR))
- Mean Heart rate (including changes from baseline (Δ HR) and from placebo and baseline ($\Delta\Delta$ HR))
- Categorical analyses for each variable and subgroup listed below:

OTcF (number and percentage of subjects, by regimen and visit)

Age	Gender	Values	
2 to < 12 years	Males and Females	< 320 ms	
		≥ 320 ms to ≤ 450 ms	oriVation
		> 450 ms to ≤480 ms	131
		> 480 ms	
12 to <18years	Males	< 320 ms	"VO.
		≥ 320 ms to ≤ 450 ms	
		> 450 ms to 500 ms	0,
		> 500 ms	XO .
12 to <18years	Females	< 320 ms) `
		≥ 320 ms to ≤ 470 ms	
		> 470ms to ≤ 500 ms	
	1	> 500 ms	
18 to 35 years	Males	< 320 ms	
	-0,3	≥ 320 ms to ≤ 450 ms	
	(0,00	> 450 ms to 500 ms	
	10,10,	> 500 ms	
18 to 35 years	Females	< 320 ms	
	N' 10 SI	≥ 320 ms to ≤ 470 ms	
	(00 10)	> 470ms to ≤ 500 ms	
	Sot	> 500 ms	

- For all ages QTcF changes from baseline (Δ QTcF, number andpercentage of subjects, by dose)

	andpercentage of su • $\leq 30 \text{ m}$		QTcF, number	
> 60 ms ORS (number and percentage of subjects, by regimen and visit)				
in on	Age	Gender	Values	
C), of	2 to <6 years	Males and Females	≤ 90 ms	
9000			> 90ms to ≤ 100 ms	
.5			>100 ms	
Y/U	6 to < 12 years	Males and Females	≤ 100 ms	

		> 100 ms to ≤ 110 ms	
		>110 ms	
12 to <18 years	Males and Females	≤110ms	0
		>110 ms to ≤ 120ms),
		>120 ms	
18 to 35 years	Males and Females	≤120 ms	
		>120 ms	
		a) 8	
PR (number and pe	rcentage of subjects, by	regimen and visit)	
Age	Gender	Values	
2 to < 6 years	Males and Females	≤ 90 ms	
		> 90 ms to ≤ 150 ms	
	4	> 150 ms	
6 to < 12 years	Males and Females	≤400 ms	
		> 100 ms to ≤ 170 ms	
		> 170 ms	

_ ` _ ' _	lecticage of Sabjects, b	
Age	Gender	Values
2 to < 6 years	Males and Females	≤ 90 ms
		> 90 ms to ≤ 150 ms
	4	> 150 ms
6 to < 12 years	Males and Females	≤ 100 ms
		> 100 ms to ≤ 170 ms
		> 170 ms
12 to <18 years	Males and Females	≤ 110 ms
	100 00 :10	> 110 ms to ≤ 180 ms
Ö	0,70 %.	> 180 ms
18 to 35 years	Males and Females	≤ 120 ms
	15 et	> 120 ms to ≤ 220 ms
O.O.	6	> 220 ms

 $_{\odot}\;$ Heart rate (number and percentage of subjects, by regimen and visit)

Age	Gender	Values
2 to <6 years	Males and Females	< 80 bpm
		≥80 bpm to ≤140bpm
illi, Ollo		> 140 bpm to ≤ 180 bpm
C AR		> 180 bpm
.5		Increase or decrease from baseline >10 bpm
		Increase or decrease from baseline > 20 bpm

		Г		
	6 to < 12 years	Males and Females	< 60 bpm	
			≥60 bpm to ≤120bpm	
			> 120 bpm to ≤ 150 bpm	76
			> 150 bpm	dilo
			Increase or decrease from baseline >10 bpm	ailation
			Increase or decrease from baseline > 20 bpm	illo
	12 to <18years	Males and Females	< 50 bpm	
			≥50 bpm to ≤100bpm	(S)
			> 100 bpm to ≤ 150 bpm	
			> 150 bpm	
		A	Increase or decrease from baseline >10 bpm	
			Increase or decrease from baseline > 20 bpm	
	18-35 years	Males and Females	< 50 bpm	
		(,,,0)	≥50 bpm to ≤100bpm	
		10,164	5 100 bpm to ≤ 150 bpm	
		8,0	> 150 bpm	
	Ö	JBI to suppose	Increase or decrease from	
	X	00 10	baseline >10 bpm Increase or decrease from	
		Sot	baseline > 20 bpm	
Zogenix ZX008-16				
Zogenix ZX008-16 ERT	601	SAP CONFIDENTIAL	Page 15 of 30 January 23, 2020	

- Overall characterization of normal and abnormal ECGs and the number and percentage of subjects with normal and abnormal ECGs. ECGs will be characterized as Normal, Abnormal Clinically Insignificant (ACI), or Abnormal
- cc.).

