 2.3.2.3 Listing for Abnormalities
 Listings for ECG abnormalities by regimen and visitwill be provided for the following:

 Heart Rates

 Sinus Tachycardia
 Sinus Bradycardia
 First degree AV-Block
 Short PR interval
 Heart Blocks
 Second degree AV-Block (Type 1)
 Second degree AV-Block (Type 2)
 Third-degree (complete) AV-Block

 QRS Duration

 PRES

- - **LBBB**
 - **RBBB**
- **QT-Interval**
- Other abnormalities seen by the over-reading cardiologist, including changes wave morphology, MI, etc.

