4.8 Categorical Analysis

Categorical data will be reported as both numbers and percentages and will include changes from baseline in both ECG and ECHO variables as detailed in section 2.3.

5 Tables, Figures, and Listings

- Table 1.1.1 Means, Mean Differences from Baseline and Upper Bound of One-Sided 95% CI from ANOVA for ECG Data QTcF, Safety Population Males and Females, 2 to <12 Years Cohort A
- Table 1.1.2 Means, Mean Differences from Baseline and Upper Bound of One-Sided 95% CI from ANOVA for ECG Data QTcF, Safety Population Males, 12 to <18Years Cohort A
- Table 1.1.3 Means, Mean Differences from Baseline and Upper Bound of One-Sided 95% CI from ANOVA for ECG Data QTcF, Safety Population Males, 18 to 35 Years Cohort A
- Table 1.1.4 Means, Mean Differences from Baseline and Upper Bound of One-Sided 95% CI from ANOVA for ECG Data QTcF, Safety Population Females, 12 to <18Years Cohort A
- Table 1.1.5 Means, Mean Differences from Baseline and Upper Bound of One-Sided 95% CI from ANOVA for ECG Data QTcF, Safety Population Females, 18 to 35 Years Cohort A
- Table 1.2.1 Means, Mean Differences from Baseline and Upper Bound of One-Sided 95% CI from ANOVA for ECG Data Heart Rate, Safety Population Males and Females, 2 to < 6 Years Cohort A
- Table 1.2.2 Means, Mean Differences from Baseline and Upper Bound of One-Sided 95% CI from ANOVA for ECG Data Heart Rate, Safety Population Males and Females, 6 to < 12 Years Cohort A
- Table 1.2.3 Means, Mean Differences from Baseline and Upper Bound of One-Sided 95% CI from ANOVA for ECG Data Heart Rate, Safety Population Males and Females, 12 to <18Years Cohort A
- Table 1.2.4 Means, Mean Differences from Baseline and Upper Bound of One-Sided 95% CI from ANOVA for ECG Data Heart Rate, Safety Population Males and Females, 18 to 35 Years Cohort A
- Table 1.3.1 Means, Mean Differences from Baseline and Upper Bound of One-Sided 95% CI from ANOVA for ECG Data QRS Duration, Safety Population Males and Females, 2 to < 6 Years Cohort A
- Table 1.3.2 Means, Mean Differences from Baseline and Upper Bound of One-Sided 95% CI from ANOVA for ECG Data QRS Duration, Safety Population Males and Females, 6 to < 12 Years Cohort A
- Table 1.3.3 Means, Mean Differences from Baseline and Upper Bound of One-Sided 95% CI from ANOVA for ECG Data QRS Duration, Safety Population Males and Females, 12 to <18 Years Cohort A

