- Table 2.2.3 Categorical Summary of ECG Data Heart Rate, Safety Population Males and Females, 12 to <18Years - Cohort A
- Table 2.2.4 Categorical Summary of ECG Data Heart Rate, Safety Population Males and Females, 18 to 35 Years - Cohort A
- Table 2.2.5 Categorical Summary of ECG Data Heart Rate Change from Baseline, Safety Population - Males and Females, 2 to <6 Years - Cohort A
- Table 2.2.6 Categorical Summary of ECG Data Heart Rate Change from Baseline, Safety Population - Males and Females, 6 to < 12 Years - Cohort A
- Table 2.2.7 Categorical Summary of ECG Data Heart Rate Change from Baseline, Safety Population - Males and Females, 12 to <18 Years - Cohort A
- Table 2.2.8 Categorical Summary of ECG Data Heart Rate Change from Baseline, Safety Population - Males and Females, 18 to 35 Years - Cohort A
- Table 2.3.1 Categorical Summary of ECG Data QRS Duration, Safety Population -Males and Females, 2 to < 6 Years - Cohort A
- Table 2.3.2 Categorical Summary of ECG Data QRS Duration, Safety Population -Males and Females, 6 to < 12 Years - Cohort A
- Table 2.3.3 Categorical Summary of ECG Data QRS Duration, Safety Population -Males and Females, 12 to <18 Years - Cohort A
- Table 2.3.4 Categorical Summary of ECG Data QRS Duration, Safety Population -Males and Females, 18 to 35 Years - Cohort A
- Table 2.4.1 Categorical Summary of ECG Data PR-Interval, Safety Population -Males and Females, 2 to < 6 Years – Cohort A
- Table 2.4.2 Categorical Summary of ECG Data PR-Interval, Safety Population -Males and Females, 6 to < 12 Years - Cohort A

Zogenix ZX008-1601 SAP Page 26 of 30 CONFIDENTIAL FRT January 23, 2020

- Table 2.4.3 Categorical Summary of ECG Data PR-Interval, Safety Population -Males and Females, 12 to <18 Years - Cohort A
- Table 2.4.4 Categorical Summary of ECG Data PR-Interval, Safety Population -Males and Females, 18 to 35 Years - Cohort A
- authorization ereof. Table 2.5.1 Categorical Summary for ECHO Data - Any PASP Findings > 35 mmHq Post-Baseline, Safety Population - Cohort A
- Table 2.5.2 Categorical Summary for ECHO Data -Any PASP Change from Baseline> 10, >15, >20 mmHg, Safety Population - Cohort A
- Table 2.6.1 Results to Support Heat Maps of Mitral Valve Results, Safety Population -Cohort A
- Results to Support Heat Maps of Mitral Valve Results, Safety Table 2.6.1.1 Population - 2 to <18 Years - Cohort A
- Results to Support Heat Maps of Mitral Valve Results, Safety Table 2.6.1.2 Population - 18 to 35 Years - Cohort A

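### The heart-rate change categories count rises and falls in one row, so they lose direction and dilute a general shift

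*SAP*

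**What the plan says.** Section 2.3.2.2 of the cardiovascular SAP sets out heart-rate categories for ages 2 to <6, 6 to <12, 12 to <18 and 18 to 35. Each age group has bands of absolute rate, such as "> 140 bpm to ≤ 180 bpm" for the youngest, followed by two change rows: "Increase or decrease from baseline >10 bpm" and "Increase or decrease from baseline > 20 bpm". Section 5 assigns the change categories to Tables 2.2.5 to 2.2.8, one per age group. A typical title is "Categorical Summary of ECG Data Heart Rate Change from Baseline, Safety Population - Males and Females, 6 to < 12 Years - Cohort A". No title mentions direction, and the table shells are not part of the document.

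The same SAP also plans heart-rate outputs that do carry direction:

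- Section 2.3.2.2 lists "Mean Heart rate (including changes from baseline" and the change against both baseline and placebo.
- Tables 1.2.1 to 1.2.4 are titled "Means, Mean Differences from Baseline and Upper Bound of One-Sided 95% CI from ANOVA for ECG Data Heart Rate, Safety Population", one per age group.
- Section 2.3.2.3 lists "Sinus Tachycardia" and sinus bradycardia as separate entries.

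**The concern.** A drug effect on heart rate usually has a direction. An upward shift produces more large rises and fewer large falls. A row that counts both adds the gain to the loss and reports only the net, and the reader cannot tell which tail moved. Elsewhere Section 2.3 works in one direction: the QTcF change categories and the PASP change thresholds (above 10, 15 and 20 mmHg) count increases.

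These rows are the cardiovascular SAP's only subject-level categories of heart-rate change. What is at stake is how informative that safety display is.

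**Working it through.** There is no planned figure to reproduce. The cardiovascular SAP gives no heart-rate SD, drug effect or test for these rows, and Section 2.4.1 says no sample size was calculated for cardiac safety. The arithmetic below is therefore an illustration.

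**Model and assumptions.** Change from baseline is normal with SD σ. Its mean is 0 on placebo and δ on drug. The base case assumes σ = 12 bpm and δ = +5 bpm. For threshold c (10 or 20 bpm, from Section 2.3.2.2):

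- rise only: P = 1 − Φ((c − δ)/σ)
- fall only: P = Φ((−c − δ)/σ)
- pooled row: the sum of the two

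**Above 10 bpm.**

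- Placebo: rise 1 − Φ(10/12) = 0.202; fall the same; pooled 0.405.
- Drug: rise 1 − Φ(5/12) = 0.338; fall Φ(−15/12) = 0.106; pooled 0.444.

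**Above 20 bpm.**

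- Placebo: rise 1 − Φ(20/12) = 0.048; pooled 0.096.
- Drug: rise 1 − Φ(15/12) = 0.106; fall Φ(−25/12) = 0.019; pooled 0.124.

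Differences below are taken before rounding.

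| Threshold | Rise only, drug vs placebo | Pooled, drug vs placebo | Share of difference kept |
|---|---|---|---|
| >10 bpm | 33.8% vs 20.2% (13.6 points) | 44.4% vs 40.5% (3.9 points) | 29% |
| >20 bpm | 10.6% vs 4.8% (5.8 points) | 12.4% vs 9.6% (2.9 points) | 50% |

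**Range.** I repeated this for σ = 10, 12, 15, 20 and δ = +3, +5, +8, +10 bpm. The extremes are:

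| Assumption | Threshold | Rise only, drug vs placebo | Pooled, drug vs placebo | Kept |
|---|---|---|---|---|
| σ 20, δ +3 | >10 | 36.3% vs 30.9% | 62.1% vs 61.7% | 7% |
| σ 10, δ +10 | >10 | 50.0% vs 15.9% | 52.3% vs 31.7% | 60% |
| σ 20, δ +3 | >20 | 19.8% vs 15.9% | 32.3% vs 31.7% | 14% |
| σ 10, δ +10 | >20 | 15.9% vs 2.3% | 16.0% vs 4.6% | 84% |

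Some of the difference is lost in every case, but the pooled row always moves upward.

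**A different pattern.** Suppose instead that 15% of subjects have a true +25 bpm effect and 85% have none, with σ = 12. A responder exceeds +20 bpm with probability 1 − Φ(−5/12) = 0.66 and almost never falls by more than 20. Above 20 bpm, rise only becomes 0.85 × 0.048 + 0.15 × 0.66 = 14.0%, against 4.8% on placebo (9.2 points). The pooled row becomes 0.85 × 0.096 + 0.15 × 0.66 = 18.0%, against 9.6% (8.5 points). About 92% is kept. Dilution is therefore mainly a problem for a shift shared by most subjects; a large effect in a few subjects survives pooling.

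**The case against.** A reader might infer that a drug that raises heart rate would be masked, or that these tables are insensitive to change in either direction. The documents do not support that. The signed mean changes, their upper bounds by age group, the separate high and low bands and the separate tachycardia and bradycardia listings would all reflect a rise. Section 9.6 of the main SAP also summarises heart rate as a vital sign, with change from baseline at each on-study evaluation. A general shift is what the mean comparison is best placed to detect. With 79 per group (the planned size in Section 2.4.1), SD 12 and +5 bpm, its illustrative power at two-sided 0.05 is about 0.75 with all ages combined. A rise-only row above 10 bpm has 0.49 and the pooled row 0.07. The plan tests none of these rows, so these figures show only relative sensitivity.

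The wording may also be shorthand for two displayed lines. The main SAP uses a similar compressed form for weight gain and reduction, and without shells a split display cannot be ruled out.

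Most of this stands, and it limits the point. It does not make the split redundant. The means describe the average and are planned by age group; with an assumed 20 per group in one stratum the same power is 0.26. The bands are wide: a subject aged 12 to 35 going from 60 to 95 bpm, or one aged 2 to <6 going from 90 to 135, stays in the middle band. Such subjects are picked up as categories only by the change rows, where they are counted with falls. Nothing in the text requires the shells to separate the two.

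**Conclusion.** The point holds as a minor one. As written, the change rows lose direction and dilute a general heart-rate shift. Under the assumed SD of 12 and +5 bpm, the contrast above 10 bpm falls from 13.6 to 3.9 points. The share kept ranges from about 7% to 60% at 10 bpm and 14% to 84% at 20 bpm over the assumed grid, and it is higher if the effect sits in a subset. All of this rests on a normal model and on inputs the SAP does not supply. Diluted is the right word, not masked. The rows are descriptive, and no sample size, error rate or primary conclusion depends on them.

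**What to change.** In Section 2.3.2.2, and in the layout of Tables 2.2.5 to 2.2.8, replace the two combined rows in each age group with four: rises above 10 bpm, rises above 20 bpm, falls above 10 bpm and falls above 20 bpm. The combined rows can stay alongside if wanted. The cost is two more rows per table, or four if the combined rows are kept. No new data are needed and no other analysis changes. If separate display was already intended, one clarifying sentence in Section 2.3.2.2 is enough.

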 2.3.2.3 Listing for Abnormalities
 Listings for ECG abnormalities by regimen and visitwill be provided for the following:

 Heart Rates

 Sinus Tachycardia
 Sinus Bradycardia
 First degree AV-Block
 Short PR interval
 Heart Blocks
 Second degree AV-Block (Type 1)
 Second degree AV-Block (Type 2)
 Third-degree (complete) AV-Block

 QRS Duration

 PRES

- - **LBBB**
 - **RBBB**
- **QT-Interval**
- Other abnormalities seen by the over-reading cardiologist, including changes wave morphology, MI, etc.

2.4 Study Population

Study ZX008-1601 includes male and female subjects, ages 2 to 35 years who met the inclusion and exclusion criteria in the protocol.

2.4.1 Sample Size

The sample size for Part 1 Cohort A was estimated under the assumption that adding ZX008 at 0.8 mg/kg/day to current therapy will lead to a mean decrease in drop seizures that is 30 percentage points greater than adding placebo to current therapy. For example, if adding placebo leads to a 10% decrease in seizures, then adding the high dose of ZX008 would be expected to decrease seizures by at least 40%. The variability expected in the trial was estimated from a Phase 3 trial of clobazam for patients with Lennox-Gastaut syndrome (Ng 2011) leading to an assumption that the standard deviation (SD) is 50%. Other assumptions include an allowance for 20% dropouts between randomization and the start of the maintenance period. Under these assumptions, a sample size of 63 subjects per treatment group for a nonparametric analysis affords 90% power to detect a difference between the ZX008 0.8 mg/kg/day and placebo groups that is significant at the q=0.05 level. Assuming a 20% drop-out rate prior to the start of the maintenance period yields a requirement for an additional 14 subjects per group for a total of 79 subjects per treatment group for a nonparametric analysis. Similar calculations for the 0.2 mg/kg/day ZX008 group lead to a total required sample size of 237. The number of subjects randomized into Part 1 Cohort A is estimated to be approximately 250 due to the long baseline period.

No formal sample size calculations were conducted related to cardiac safety for Study 1601.

2.5 Randomization and Treatments

Upon completion of the Baseline Period in Part 1, subjects who qualified for the study were randomized (1:1:1) in a double-blind manner to receive 1 of 2 doses of ZX008 (0.2 mg/kg/day, 0.8 mg/kg/day; 30mg/day maximum [0.2 mg/kg/day or 0.5 mg/kg/day; 20 mg/day maximum for subjects taking concomitant STP]) or placebo. The randomization was stratified by weight (<37.5 kg, $\ge 37.5 \text{ kg}$) to at, arms, a a rando. It qualified fc ensure balance across treatment arms, with a target of at least 25% in each weight group. Subjects were assigned a randomization number by the IWR system upon confirmation that the subject qualified for enrollment in the Titration Period.

3 Cardiac Safety Data Collection and Analysis

3.1 ECG Assessment

Journal of ECGs

3.1.3 Collection of ECGs

The clinical ECG database will be derived from 12-lead ECGs collected from the ELI-150c ECG machines.

Single, 12-lead ECGs were collected in Part 1 at:

Screening (Visit 1)

Randomization (Visit 3)

Maintenance Period (Study Day 43, Visit 8)

EOS/ET (Visit12)

Follow-up (Visit 14)

Unscheduled

Gs were collected after the subjects had been in supine or nutes.

time of the ECG was not controller.

3.1.4 Definition of Baseline

The baseline for this study will be the data collected from the ECG taken at Randomization (Visit 3).

3.1.5 Variables Measured

At the central laboratory, using CAMI software, the cardiac technician will annotate the Global Superimposed Median Beat (GSMB).

The following variables will be measured or calculated on each ECG:

- ORS duration
- PR interval
- Heart rate (10 second average)
- QT
 - The QT interval will be measured from the earliest detection of depolarization in any lead (peak of the Q or R wave) to the latest

detection of repolarization in any lead (end of the T-wave).

QTcF

The RR interval will be reported, from which the corrected QT interval (QTc) using

Fridericia's correction:
$$QTcF = -$$

Joinds.

Joings.

Joi

3.2 Echocardiographic Analysis

3.2.1 Equipment

Site-owned equipment was used for the collection of echocardiograms.

Prior to being qualified for subject enrollment, all echocardiographers were required to participate in a WebEx PowerPoint training presentation and transfer test data to ERT. The WebEx session consisted of reviewing protocol specific views, study related forms and the process of uploading the images through web portal.

Each echocardiographer who had not been previously certified for a Zogenix study was required to submit a certification ECHO. The certification ECHOwas performed on a non-study participant. The participating ECHO facility was informed during the training session that they would not be able to perform ECHOs on true study subjects until they received a "passed" Certification ECHO Evaluation Form. Previously certified echocardiographers were exempt.

3.2.2 Transfer of Echocardiograms

Echocardiograms were either digitally transferred or copied to CD and sent via courier to ERT for analysis.

3.2.3 Collection of Echocardiograms

ECHOs in Part 1 were performed at:

- Screening (Visit 1)
- Maintenance Period (Visit 8; between Study Day 40 and 54)
- EOS/ET (Visit 12; between Study Day 90 and Study Day 113)
- Follow-up (Visit 14)
- Unscheduled

The time of the ECHO was not controlled.

